4.2 Justification for Dose

Valacyclovir oral suspension has been evaluated in GlaxoSmithKline-sponsored studies in children 1 month to 12 years of age (8), but not in neonates (infants under 1 month of age). In the U.S., valacyclovir is licensed for the treatment of pediatric patients with orolabial HSV recurrences (12 years and older) and chickenpox (2 years through 17 years of age). Pediatric valacyclovir dosing is 20 mg/kg per dose (dose not to exceed 1 gram) administered either three times a day (for VZV) or twice a day (for HSV) (8). Valacyclovir has demonstrated an excellent safety profile over the 20 years since its initial approval in the U.S. In order to minimize the likelihood of neutropenia or elevated creatinine in the study population, the starting valacyclovir dose regimen in this study will be 10 mg/kg/dose, which is one-third of the FDA-approved dose for children 2 years of age and older of 20 mg/kg/dose administered three times per day. Each subject will be carefully monitored for bone marrow toxicity (e.g., neutropenia) and nephrotoxicity (e.g., elevated creatinine) and the drug will be stopped if significant toxicities are encountered in a given subject.

5. STUDY POPULATION

Neonates delivered to mothers receiving oral valacyclovir therapy (or equivalent antiviral drug) for suppression of genital HSV recurrences at the end of pregnancy will be enrolled within the first two days of life.

5.1 Inclusion Criteria

To be eligible to participate in this study, an individual must meet all of the following criteria:

- Signed informed consent from parent(s) or legal guardian(s)
- Maternal history of genital HSV infection
- Maternal receipt of oral acyclovir, valacyclovir, or famciclovir suppressive therapy for ≥ 7 days prior to delivery
- Gestational age ≥ 38 weeks at birth
- ≤ 2 days of age at study enrollment*
- Weight at study enrollment $\geq 2,000$ grams

* For purposes of this study, the calendar day of birth is Day of Life 0

5.2 Exclusion Criteria

An individual who meets any of the following criteria will be excluded from participation in this study:

- Evidence of neonatal HSV infection
- Evidence of sepsis
- Known renal anomalies or dysfunction
- Maternal genital lesions suspicious for HSV at the time of delivery
- Infants known to be born to women who are HIV positive (but HIV testing is not required for study entry)
- Current receipt in the neonate of acyclovir, ganciclovir, famciclovir, or any investigational drugs

5.2.1 Exclusion of Specific Populations

This pediatric study will not exclude young children, females, or minorities. This study will be inclusive of all children who meet the inclusion/exclusion criteria, regardless of religion, gender, or ethnic background.

5.3 Inclusion of Vulnerable Participants

Not applicable

5.4 Lifestyle Considerations

Not applicable

5.5 Screen Failures

The investigator or designee is to review the inclusion/exclusion criteria and determine the subject's eligibility for study participation. Only the following information will be collected on screen failures: demographics (age, screen number, sex, ethnicity, and race) and reason for ineligibility. The parent(s)/guardian(s) of subjects who are found to be ineligible will be told the reason for ineligibility.

5.6 Strategies for Recruitment and Retention

5.6.1 Recruitment

Each site participating in this study will develop an individual recruitment plan that is specific to their region and facility requirements. Recruitment materials may be delivered in prenatal and postnatal settings.

5.6.2 Retention

Enrolled subjects will be followed for only 42 days. Challenges with subject retention are therefore not anticipated.

5.6.3 Compensation Plan for Subjects

Study subject compensation, if any, will be determined by the individual sites. The compensation plan will be in accordance with local IRB requirements and subject to local IRB approval.

5.6.4 Costs

There is no cost to subjects for the research tests, procedures, and study product while taking part in this trial. Procedures and treatment for clinical care may be billed to the subject, subject's insurance or third party.

6. STUDY PRODUCT

6.1 Study Product(s) and Administration

6.1.1 Study Product Description

Valacyclovir hydrochloride (Valtrex) is a white to off-white powder (from tablets) of the hydrochloride salt of the L-valyl ester of acyclovir with the molecular formula $C_{13}H_{20}N_6O_4 \cdot HCl$ and a molecular weight of 360.80. Each 500 mg tablet (blue, film-coated) contains valacyclovir hydrochloride equivalent to 500 mg valacyclovir and the inactive ingredients carnauba wax, colloidal silicon dioxide, crospovidone, FD&C Blue No. 2 Lake, hypromellose, magnesium stearate, microcrystalline cellulose, polyethylene glycol, polysorbate 80, povidone, and titanium dioxide (18). Valacyclovir tablets will be extemporaneously compounded as an oral suspension using SyrPalta as the oral liquid vehicle (13). SyrPalta syrup vehicle contains sucrose 83% w/v; Purified Water; Glycerin; Artificial Flavors; 0.2% Alcohol; 0.1% Sodium Benzoate; 0.001% Benzalkonium Chloride as a Preservative. It is the recommended oral liquid vehicle for

valacyclovir suspension from the extemporaneous compounding references supported by the FDA Safe Use Initiative: the Michigan Pediatric Safety Collaboration (<https://www.mipedscompounds.org/>), and the American Society of Health System Pharmacists (ASHP) Standardize 4 Safety Initiative (<https://www.ashp.org/-/media/assets/pharmacy-practice/s4s/docs/Compound-Oral-Liquid.ashx>).

6.1.2 Dosing and Administration

The shelf-life of valacyclovir oral suspension following preparation is 28 days in the refrigerator between 2°C to 8°C (36°F to 46°F). Study product will be administered by the parent/guardian if subjects are at home, or by the hospital staff if subjects are in the hospital. Study Cohort 1 will receive valacyclovir at a dose of 10 mg/kg body weight administered two times daily for 5 days, while the dose evaluated in Cohort 2 will be predicated upon the exposure levels of subjects enrolled in Cohort 1. Specific dosing volumes will be provided for each subject based on body weight and valacyclovir oral suspension concentration. Valacyclovir Oral Suspension will be administered into the subject's mouth via an oral dosing syringe. The parent/guardian will be provided with specific dosing, storage, and administration instructions. If the subject vomits or spits up following the dosing, re-dosing for that dose is not allowed.

Table 3. Dosing and Administration

Cohort	Product Name	Dose	Route	Frequency of Administration	Duration of Therapy
1	Valacyclovir	10 mg/kg	Oral	bid	5 days
2	Valacyclovir	TBD	Oral	bid	5 days

6.1.3 Dose Escalation

Dose selection for Cohort 2 will be predicated upon the pharmacokinetic data from Cohort 1. Specifically, the target range of acyclovir exposure is between 24,000 ngxh/mL and 48,000 ngxh/mL. If the mean of observed acyclovir exposures of subjects in Cohort 1 are below 24,000 ngxh/mL, AND if no Grade 3 or Grade 4 AEs or SAEs are detected in any of the study subjects, then the 8 subjects enrolled in Cohort 2 will receive oral valacyclovir at a dose of 20 mg/kg administered two times daily for 5 days. Alternatively, if the mean of observed acyclovir exposures of subjects in Cohort 1 are above 48,000 ngxh/mL AND if no Grade 3 or Grade 4 AEs or SAEs are detected in any of the study subjects, then the 8 subjects enrolled in Cohort 2 will receive oral valacyclovir at a dose that has been linearly adjusted downward to target 36,000 ngxh/mL area-under-the-concentration-time curve from 0 to 12 hours (AUC₁₂). If the mean of observed acyclovir exposures of subjects in Cohort 1 are within the target range of 24,000 ngxh/mL to 48,000 ngxh/mL, Cohort 2 will not be opened for enrollment unless suggested by the Safety Monitoring Committee (SMC) (see [Section 9.4.6](#)).

If the targeted exposure is not achieved in Cohorts 1 and 2 and the safety data are acceptable, it is possible, but not anticipated, that additional dosing cohorts could be recommended based upon the results of subjects in the first two cohorts. If such a recommendation is made, dose selection and subject enrollment and assessment will follow the approach used for Cohort 2.

6.1.4 Dose Modifications

Valacyclovir will be dosed according to the study cohort into which the subject enrolls. Study Cohort 1 will receive 10 mg/kg body weight administered two times daily for 5 days, while the dose for Cohort 2 will be predicated upon the pharmacokinetic results of subjects enrolled in Cohort 1, as detailed in [Section 4](#).

6.2 Preparation/Handling/Storage/Accountability

6.2.1 Acquisition and Accountability

Acquisition:

Commercial brand name (Valtrex) valacyclovir (500 mg tablets) and SyrPalta syrup vehicle will be shipped to the participating sites from the DMID Clinical Material Services (CMS). Ancillary supplies for oral administration, such as amber bottles and oral dosing syringes, will be provided by the clinical research site. Multiple lots may be provided. The study products will be open label and not kit specific. Extemporaneous preparation of the suspension formulation will be performed by the site's research pharmacist following enrollment of a subject (13).

Accountability:

After receipt of the study product, the site principal investigator (PI) is responsible for study product distribution and disposition and has ultimate responsibility for study product accountability. The Site PI will delegate to the site Research Pharmacist the responsibility for study product accountability. Each pharmacist will be responsible for and will maintain logs of receipt, accountability, dispensation, storage conditions, and disposal of study drug. All study product, whether administered or not, must be documented on the appropriate study product accountability record or dispensing log. Parents/guardians will be instructed to return the used bottle and medication diary to the PI at Study Day 5.

Unused (e.g., returned) study product will be retained at the site until further instruction from the Sponsor or its designee. Upon study completion, or termination and final monitoring visit, the Sponsor or its designee will provide instructions for the return of any remaining unused study product to the repository or destroyed according to site procedures with a second staff member observing and verifying the destruction. Used study product will be destroyed at the site in accordance with standard site procedures following monitoring and release for destruction, unless the site's local storage policy prohibits retention of used IP. In that event, used study product may be destroyed on-site following applicable site procedures with a second staff member observing and verifying the destruction.

At study completion, the sites will be required to return the drug accountability log to the UAB Central Unit (CU) upon request, retaining a copy of the drug accountability form in their study files.

6.2.2 Formulation, Appearance, Packaging, and Labeling

Commercial valacyclovir tablets 500 mg (Valtrex) will be supplied for extemporaneous preparation of the suspension formulation by the Research Pharmacist. Valacyclovir

hydrochloride is a white to off-white powder (from tablets) of the hydrochloride salt of the L-valyl ester of acyclovir. The blue, film-coated tablets are printed with edible white ink. Commercial SyrPalta will be supplied as the vehicle for the valacyclovir suspension and is a clear liquid (13). Valacyclovir oral suspension will be stored in an amber medicine bottle with a child-resistant closure. The final prepared oral suspension will be labeled with the FDA-required cautionary statement “Caution: New Drug Limited by Federal Law to Investigational Use”.

6.2.3 Product Storage and Stability

Valacyclovir tablets will be stored at 15°C to 25°C (59°F to 77°F). SyrPalta syrup vehicle will be stored between 13°C to 29°C (56°F to 85°F). The final prepared valacyclovir oral suspension will be stored refrigerated between 2°C and 8°C (36°F to 46°F) in the pharmacy and subject’s home. Shake well before using. Discard after 28 days.

6.2.4 Preparation

Valacyclovir Oral Suspension will be extemporaneously prepared by the site Research Pharmacist following the instructions in the Manual of Procedures for dispensing to the study subject. One bottle will be compounded and dispensed at study enrollment and will suffice for the full 5-day treatment period. Resupply will only be provided in the event of loss of the product by the family. Additional details regarding preparation and procedures for dispensing or administration of study product will be described in the protocol-specific Manual of Procedures.

6.3 Measures to Minimize Bias: Randomization and Blinding

6.3.1 Treatment Assignment Procedures

Not applicable. All subjects will receive study product.

6.3.2 Randomization and Blinding

Not Applicable

6.3.3 Blinding and Masking Procedures

Not applicable. No masking procedures will be done.

6.4 Study Intervention Compliance

Assessment of compliance with administration of study medication throughout the 5-day treatment period will be achieved by utilization of a medication diary. The parent(s) or legal guardian(s) will complete this diary daily, indicating the time of drug administration and whether the subject vomited following the dose. The diary will also note the storage conditions of the product (e.g. refrigerated). The diary will be collected at the Study Day 5 visit.

6.5 Concomitant Therapy

Concomitant medications will be recorded on the specified CRF at Study Visit Days 1, 5, 10, and 42.

6.5.1 Rescue Medicine

Not applicable

7. STUDY INTERVENTION DISCONTINUATION AND PARTICIPANT DISCONTINUATION/WITHDRAWAL

7.1 Halting Criteria and Discontinuation of Study Intervention

7.1.1 Study Halting Criteria

Enrollment and study product administration will be halted for SMC review/recommendation if any of the following is reported:

- Any subject experiences an SAE after study product administration that is considered related to the study product.
- Two subjects experience an AE Grade 2 or higher from the same organ class, deemed to be a study product-related unsolicited AE.
- Two subjects experience the same Grade 2 or higher study product-related safety laboratory AE.

Additionally, DMID and the Central Unit may interrupt study dosing and/or study entry at any time if medically indicated. To minimize risk, the medical monitor will review real-time safety data and the SMC will review cumulative safety data. If enrollment is halted based upon the study halting criteria above or the review of the safety data, upon completion of the review and receipt of advice of the SMC, DMID and the Central Unit Administration will determine if study entry or study dosing may continue according to the protocol.

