7.1.2 Individual Halting Criteria

Subjects with any initial (pre-dosing) hematology or chemistry safety lab that is \geq Grade 1 in value utilizing the DAIDS Toxicity Tables ([Appendix A](#)) will be withdrawn from the study and will not receive study medication. During the 5 days of study product dosing, a Grade 2 or higher AE, including a laboratory AE, will result in halting of study product administration for the subject. If a subject develops signs/symptoms of HSV infection, study medication will be stopped and standard antiviral therapy will be administered.

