7.1.3 Criteria for Continuation of Dosing and Redosing

In the event a halting rule is met:

- An unscheduled safety analysis by the SMC will be required for approval of further enrollment, and
- Further administration of the study product is suspended for ALL subjects until an assessment by the SMC takes place.

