8.4.2 Definition of Serious Adverse Events

An SAE is defined as an adverse event or suspected adverse reaction is considered "serious" if, in the view of either the investigator or sponsor, it results in any of the following outcomes:

- Death,
- A life-threatening adverse event*;
- Inpatient hospitalization or prolongation of existing hospitalization;
- A persistent or significant incapacity or substantial disruption of the ability to conduct normal life functions; or
- A congenital anomaly/birth defect.

* Life-threatening adverse event. An adverse event is considered “life-threatening” if, in the view of either the investigator or sponsor, its occurrence places the patient or subject at immediate risk of death. It does not include an adverse event that, had it occurred in a more severe form, might have caused death. It does not necessarily include all grade 4 AEs according to the toxicity tables in [Appendix A](#).

Important medical events that may not result in death, be life-threatening, or require hospitalizations may be considered serious when, based upon appropriate medical judgment they may jeopardize the patient or subject and may require medical or surgical intervention to prevent one of the outcomes listed in this definition. Examples of such medical events include allergic bronchospasm requiring intensive treatment in an emergency room or at home, blood dyscrasias or convulsions that do not result in inpatient hospitalization, or the development of drug dependency or drug abuse.

All SAEs will be:

- Recorded on the appropriate SAE eCRF;
- Followed through resolution or stabilization by a licensed study physician (listed on the Form 1572 as the site PI or Sub-Investigator);
- Reviewed and evaluated by DMID, and will be sent to the SMC (for periodic review) and the IRB.

Relationship to Study Products: The physician’s assessment of an AE's relationship to valganciclovir study drug is part of the documentation process, but it is not a factor in determining what is or is not reported in the study. If there is any doubt as to whether a clinical observation is an AE, the event should be reported. All AEs must have their relationship to study product assessed using the terms “related” or “not related,” and should be followed through resolution or stabilization. In a clinical trial, the study product must always be suspect.

The investigator must provide an assessment of relationship of AEs to the study product based on:

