8.4.3.1 Severity of Event

All reportable AEs will be graded by the investigator according to the protocol toxicity tables ([Appendix A](#)) using a four-grade system ([Table 1](#)). For safety laboratory results with an absolute number in the toxicity tables (e.g., hemoglobin), grading of the AEs will be according to the toxicity tables and not according to the local laboratory reference range. For safety laboratory results with a reference to the Upper Limit Normal (ULN) in the toxicity tables (e.g., ALT or SGPT), grading of the AEs will utilize the ULN of the local laboratory reference range in determining grading of the event per the toxicity tables. Grade 4 AEs will be only reported as SAE if the event meets one of the regulatory definitions of SAE described below based on the study site physician judgment. The functional table below should be used to grade the severity of an AE that is not specifically identified in the grading table. In addition, all deaths related to an AE are to be classified as grade 5.

Table 4. Protocol Toxicity Table

(Four-grade system utilized for this trial [see also [Appendix A](#)])

PARAMETER	GRADE 1 MILD	GRADE 2 MODERATE	GRADE 3 SEVERE	GRADE 4 POTENTIALLY LIFE- THREATENING
Clinical adverse event NOT identified elsewhere in the grading table	Mild symptoms causing no or minimal interference with usual social & functional activities with intervention not indicated	Moderate symptoms causing greater than minimal interference with usual social & functional activities with intervention indicated	Severe symptoms causing inability to perform usual social & functional activities with intervention or hospitalization indicated	Potentially life- threatening symptoms causing inability to perform basic self-care functions with intervention indicated to prevent permanent impairment, persistent disability, or death

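### A single related Grade 3 or 4 AE not classed as serious brings no trial-level halt and no mandatory SMC review, while related Grade 2 events in two subjects bring both

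*Protocol*

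**What the plan says.** Protocol 7.1.1 halts enrollment and dosing for SMC review on any of three findings: one subject with a related SAE; two subjects with related unsolicited AEs of Grade 2 or higher in one organ class; or "Two subjects experience the same Grade 2 or higher study product-related safety laboratory AE". Section 7.1.3 begins "In the event a halting rule is met", then requires an unscheduled SMC analysis before further enrollment and states: "Further administration of the study product is suspended for ALL subjects until an assessment by the SMC takes place".

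Grade and seriousness are kept apart. Section 8.4.3.1 says "Grade 4 AEs will be only reported as SAE if the event meets one of the regulatory definitions of SAE". Section 8.4.2 leaves room for judgement: an important medical event may be called serious if it "may jeopardize the patient or subject and may require medical or surgical intervention to prevent one of the outcomes listed in this definition", and blood dyscrasias are among the examples.

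For a single event that is not an SAE, the plan provides the following:
- **Protocol 7.1.2:** "During the 5 days of study product dosing, a Grade 2 or higher AE, including a laboratory AE, will result in halting" of study product in that subject.
- **Protocol 7.1.1:** "the medical monitor will review real-time safety data and the SMC will review cumulative safety data", and "DMID and the Central Unit may interrupt study dosing and/or study entry at any time if medically indicated".
- **Protocol 10.1.6 and SAP 6.6:** the SMC meets ad hoc when the trial-level halting criteria are met or when DMID asks. Under 10.1.6 its scheduled review follows each cohort of 8, after dosing and 42 days of follow-up, and enrollment does not wait for it.
- **Protocol 6.1.3 and 9.4.6:** the pre-set dose change for Cohort 2 requires that no subject has had a Grade 3 or 4 AE or an SAE, whatever the cause.

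SAP 4.4.5 records that Cohort 2 was opened at 20 mg/kg twice daily.

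**The concern.** The halting rule ranks a less severe signal above a more severe one. The same related Grade 2 creatinine rise in two infants stops the trial and brings in the SMC. A related Grade 4 rise in one infant, if not judged serious, requires neither.

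The events concerned are the ones the protocol worries about most. Section 2.3.1 names neutropenia and creatinine elevation as the main toxicities of parenteral acyclovir in young infants. It reports neither with oral valacyclovir from one month of age. However, section 2.2.1 says that no neonates have been studied, and the only regimen it lists below one year of age is a single 25 mg/kg dose.

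Safety laboratory tests are scheduled on Study Days 1 and 5, and drug stops after the Day 5 PK samples. An abnormality at a scheduled draw is therefore found as that infant's own dosing ends. Prompt SMC review would mainly protect the other infants in the cohort who are being dosed or have yet to start.

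**Working it through.** The documents state no halting probability, so there is no planned figure to reproduce. The check is first of logic, then of size.

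**Step 1. Apply 7.1.1 to two cases.**

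| Criterion in 7.1.1 | One subject, one related non-serious Grade 3 or 4 AE | Two subjects, same related Grade 2 AE |
|---|---|---|
| One related SAE | Not met | Not met |
| Two subjects, related Grade 2+ unsolicited AE, same organ class | Not met (one subject) | Met, if the AE is of this type |
| Two subjects, same related Grade 2+ laboratory AE | Not met (one subject) | Met, if a laboratory AE |
| Trial-level halt and mandatory SMC review | No | Yes |

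The pair must be in two different subjects; two Grade 2 events in one infant trigger nothing. A Grade 3 or 4 event does count as one half of a pair.

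**Step 2. Which events fall through.** Many clinical Grade 3 or 4 events would be SAEs, for example through hospitalization, and severe neutropenia might be classed as serious by judgement under 8.4.2. Appendix A grades laboratory events on numbers alone. Creatinine at 3.5 times ULN or more, or at least a 2.0-fold increase over baseline, is Grade 4 with no symptom required. What remains is mainly asymptomatic creatinine, ALT or ANC events, plus Grade 3 clinical events without hospitalization.

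**Step 3. Who is left uncovered.** The dose-change condition and the scheduled SMC review act between cohorts. Within a cohort of 8, after one infant's event, 0 to 7 others may be on drug or not yet dosed. The documents do not fix this number.

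**Step 4. Size.** Assume one event type, 8 independent infants, Grade 3/4 rate p and Grade 2 rate q per infant, with all events related and none serious. Exactly one Grade 3/4 event and no Grade 2 event, so no halt, has probability

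8 × p × (1 − p − q)^7.

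| p | q = 0 | q = p |
|---|---|---|
| 1% | 8 × 0.01 × 0.99^7 = 7.5% | 8 × 0.01 × 0.98^7 = 6.9% |
| 5% | 8 × 0.05 × 0.95^7 = 27.9% | 8 × 0.05 × 0.90^7 = 19.1% |
| 10% | 8 × 0.10 × 0.90^7 = 38.3% | 8 × 0.10 × 0.80^7 = 16.8% |

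Section 7.1.1 sets no per-cohort limit on the pair, so a related Grade 2 event in Cohort 1 can pair with a Cohort 2 event. Take Cohort 1 to have had no Grade 3/4 event of this type (in line with the dose-change condition) and the same rates in both cohorts. The result is then multiplied by the chance of no Grade 2 event in Cohort 1, (1 − q/(1 − p))^8. With q = p:
- p = 5%: 0.191 × (0.90/0.95)^8 = 0.191 × 0.649 = 12.4%.
- p = 10%: 0.168 × (0.80/0.90)^8 = 0.168 × 0.390 = 6.5%.

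With q = 0 nothing changes.

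**The case against.** The best defence is that the plan does not ignore such an event. Drug is stopped in the affected infant, the medical monitor sees the data in real time, and DMID can interrupt the trial or call the SMC. One Grade 3 or 4 AE of any cause blocks the pre-set dose change. Further cohorts need acceptable safety data, and the SMC reviews each cohort. Asking for a second subject before a halt is also defensible when 8.4.3.2 lets a temporal relationship alone make an event related. All of this stands. It explains why no automatic halt is needed, but it does not make referral to the SMC mandatory within a cohort.

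The assumed rates are also open to challenge, because the documents give none for neonates. If the report of no neutropenia or creatinine elevation is read as 0 events in the 112 children of 2.2.1 (the denominator is an assumption), the upper 95% limit is 1 − 0.05^(1/112) = 2.6% one-sided, or 1 − 0.025^(1/112) = 3.2% two-sided. The 5% and 10% rates lie above that limit. But none of those children were neonates and not all had repeat dosing, so the limit cannot be carried over either.

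Three stronger readings are tempting and should be set aside:
- **A later cohort could open without the SMC knowing of the event.** The dose-change condition and the post-cohort review prevent that.
- **7.1.3 suspends everyone after one individual stop under 7.1.2.** Section 10.1.6 speaks of trial-level criteria. On the other reading one Grade 2 AE in an infant on drug would suspend all dosing, leaving the two-subject criteria without a role during dosing. The unclear wording is editorial.
- **A Grade 4 laboratory event can never trigger a halt.** It can, if it is related and judged serious, or if a second subject has a matching event.

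**Conclusion.** The point holds as a gap within a cohort. A single product-related, non-serious Grade 3 or 4 AE carries no guaranteed SMC review before the remaining infants in that cohort are exposed, while a milder pair in two subjects does. It applies to infants in Cohort 2 at 20 mg/kg who are on drug or not yet dosed (0 to 7, not known from the documents), and to any further cohort once it is open.

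The probabilities rest on assumed rates, one event type, independence, and every event being related and non-serious. The zero-Grade-2 figures are the maximum at each rate, and they fall where Grade 2 events also occur or carry over from Cohort 1. They show that a lone event is a plausible course of events; they do not estimate this trial's risk. The SMC charter was not available and may already close the gap. This is a cheap improvement to make, not a flaw that undermines the trial.

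**What to change.** Add to the ad hoc list in Protocol 10.1.6, and to SAP 6.6, that any single product-related AE of Grade 3 or higher, including a laboratory AE, is sent promptly to the existing SMC for review. There would be no automatic halt; DMID decides on the SMC's advice. If the SMC charter already requires this, a cross-reference in 10.1.6 is enough. While the text is open, 7.1.3 could say that it refers to the 7.1.1 criteria.

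The cost is a short amendment with Single IRB approval (Protocol 10.1) and an occasional review of what proves to be a chance event. Expected referrals per cohort of 8 and per event type are 8p: 0.08 at a 1% rate, 0.4 at 5% and 0.8 at 10%.
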